8.2 SAFETY ASSESSMENTS

The main anticipated adverse effect for the combination of SAR444245 with other anticancer therapies includes manifestations of cytokine release that can range from fever to hypoxia to hypotension, with or without manifestations that may include any of the organ systems. These mild events occur between around 12 to 18 hours after the first administration and a more intensive monitoring of vital signs is planned during that period. Targeted physical exams and standard laboratory tests will be conducted to monitor potential changes in the main body functions. Measurement of cytokines in plasma are planned at relevant timepoints. White blood cell differential count will be measured to monitor for transient lymphopenia which is commonly observed in the first few days following SAR444245 infusion. Eosinophilia that is surrogate to VLS will also be monitored. IL-5, which is also a marker of VLS, will be included in the PD_y cytokine panel. When clinically indicated, on-treatment ECG, LVEF, and troponin will be assessed and compared to baseline. More details on the safety assessment are provided below. Planned time points for all safety assessments are provided in the SoA.

8.2.1 Physical examinations

- A full physical examination will include, at a minimum, assessments of the cardiovascular, respiratory, gastrointestinal, neurological, and skin systems. Height and weight will also be measured and recorded.
- A directed physical examination will include, at a minimum, assessments of the skin, lungs, cardiovascular system, and abdomen (liver and spleen).
- Investigators should pay special attention to clinical signs related to previous serious illnesses. Investigators should also pay attention to clinical signs suggestive of VLS, such as peripheral edema, pericardial effusion, and pleural effusion, as well as clinical signs suggestive of immune-related adverse events, such as pneumonitis, colitis, endocrinopathies, to name a few. Complementary assessments should be performed to establish the diagnosis when clinically indicated. Early signs of cytokine release syndrome should also prompt a thorough clinical assessment to identify the involvement of a specific organ system, including neurological system.

8.2.2 Vital signs

- Temperature, pulse rate, respiratory rate, and blood pressure will be assessed.
- Blood pressure and pulse measurements should be preceded by at least 5 minutes of rest for the participant in a quiet setting without distractions (eg, television, cell phones).

- Vital signs including temperature, pulse rate, respiratory rate, and blood pressure will be assessed after 5 minutes rest
- At Cycle 1 Day 1, vital signs after infusion initiation will be collected more intensively; vital signs will be measured at Pre-dose, 0.5 (± 0.25), 1 (± 0.25), 2 (± 0.5), 4 (± 0.5) hours after start of SAR444245 dose in an in-patient setting.
- At Investigator's discretion, participants may have intensive vital sign monitoring: to be measured at Pre-dose, 0.5 (± 0.25), 1 (± 0.25), 2 (± 0.5), 4 (± 0.5), 8 (± 0.5), 12 (± 1), 16 (± 1), 20 (± 1), 24 (± 1) hours after start of SAR444245 dose in an in-patient setting.
- From Cycle 2 to Cycle 4 study therapy will be administered for all participants in out-patient clinic with vital signs taken at baseline, at least 4 to 6 hours after the start of SAR444245 dosing, or for longer periods of time if clinically indicated.
- From Cycle 5, vital signs will be measured at Pre-dose.

8.2.3 Electrocardiograms and LVEF

- Includes single 12-lead ECG, LVEF, and troponin that will be performed at screening and troponin at Cycle 4 Day 1, then, as clinically indicated.
- At Cycle 1 Day 1, ECG will be obtained, at pre-dose and at end of SAR444245 infusion.
- LVEF evaluation will be done by echocardiography or multigated acquisition (MUGA), and any repeated assessment should be done with the same technology used at screening.
- Additional evaluations such as ECG, LVEF, Holter monitoring, cardiac enzymes (such as troponin) and consultation with a cardiologist should be done when clinically indicated.
- During treatment, or post treatment follow-up: Troponin will be performed at Cycle 4 Day 1. In case of a suspicion of a drug related cardiac event (eg, including signs/symptoms of cardiac disease, ECG and/or echo changes, troponin elevation, etc.), Investigators are encouraged to do ECG, echocardiography and/or cardiac biomarker tests, as medically indicated, including cardiology consultation.

8.2.4 Clinical safety laboratory assessments

- See Appendix 2 ([Section 10.2](#)) for the list of clinical laboratory tests to be performed and to the SoA ([Section 1.3](#)) for the timing and frequency.
- The clinical safety laboratory assessments will be done in the local laboratory.
- The Investigator must review the laboratory report, document this review, and record any clinically relevant changes occurring during the study as an AE. The laboratory reports must be filed with the source documents. Abnormal laboratory findings associated with the underlying disease are not considered clinically significant, unless judged by the Investigator to be more severe than expected for the participant's condition.

- All laboratory tests with values considered clinically significantly abnormal during participation in the study or within Follow-Up Visit 1 should be repeated until the values return to normal or baseline or are no longer considered clinically significant by the Investigator or Sponsor.
 - If such values do not return to normal/baseline within a period of time judged reasonable by the Investigator, the etiology should be identified, and the Sponsor notified.
 - All protocol-required laboratory tests, as defined in Appendix 2 ([Section 10.2](#)), must be conducted in accordance with the laboratory manual and the SoA ([Section 1.3](#)).
 - If laboratory values from non-protocol specified laboratory tests performed at the institution's local laboratory require a change in participant management or are considered clinically significant by the Investigator (eg, SAE or AE or dose modification), then the results must be recorded.

8.2.5 Pregnancy testing

- Refer to [Section 5.1](#) Inclusion criteria I 03 for pregnancy testing criteria; the Investigator is responsible for review of medical history, menstrual history, and recent sexual activity to decrease the risk for inclusion of a woman with an early undetected pregnancy.
- Women of childbearing potential must have a negative urine pregnancy test result within 72 hours prior to first IMP administration of each cycle, at EOT and every 30 (± 7) days until 120 days (for Cohort A, B1, B2, B3, C, and D1) or 60 days (for Cohort D2) after the last dose of study treatment. If urine pregnancy results cannot be confirmed as negative, a serum pregnancy test will be required. Pregnancy tests (serum and/or urine tests) should be repeated if required by local guidelines.

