1.3 SCHEDULE OF ACTIVITIES (SOA)

Evaluation ^a	Screening	Treatment Period ^b				End of Treatment	Observation Period ^c			Survival Phone Call Follow-up ^d	Notes
		Cycle 1		Cycle 2 and beyond ^e			EOT Visit	Follow-Up	Follow-Up	Follow-Up	
		Visit 1	Visit 2	Visit 3+				Phone Call FU			
Cycle Day (Visit window in Days)	D-28 to D-1	D1	D8 ^f (±1)	D15 ^f (±1)	D1 (±3)	30 days (+/- 7 days) after last IMP or at initiation of further therapy	3 months after last IMP admin ±7 days	6 months after last IMP admin ±7 days	Every 3 months after FU visit 2 ± 7 days	Every 3 months +/- 14 days	
Informed consent	X										
Inclusion and exclusion criteria	X										
IRT contact	X	X			X	X					
Demography, medical/surgical and disease history	X										See Section 8
Body Weight / Height ^g	X	X	X	X	X	X	X				
Full physical examination	X					X					See Section 8.2.1
Directed Physical examination		X	X	X	X		X				See Section 8.2.1
Vital Signs	X	X	X	X	X	X	X				See Section 8.2.2
Performance status (ECOG)	X	X	X	X	X	X	X				
SpO ₂	X	As clinically indicated									

Evaluation ^a	Screening	Treatment Period ^b				End of Treatment	Observation Period ^c			Survival Phone Call Follow-up ^d	Notes
		Cycle 1			Cycle 2 and beyond ^e		Follow-Up	Follow-Up	Follow-Up		
		Visit 1	Visit 2	Visit 3+			Phone Call FU				
Cycle Day (Visit window in Days)	D-28 to D-1	D1	D8 ^f (±1)	D15 ^f (±1)	D1 (±3)	30 days (+/- 7 days) after last IMP or at initiation of further therapy	3 months after last IMP admin ±7 days	6 months after last IMP admin ±7 days	Every 3 months after FU visit 2 ± 7 days	Every 3 months +/- 14 days	
Laboratory and other investigations											
12-Lead ECG	X	X	As clinically indicated								See Section 8.2.3
LVEF	X	As clinically indicated									See Section 8.2.3
Troponin	X	As clinically indicated		X (Cycle 4 Day 1)	As clinically indicated						See Section 8.2.3 and Section 10.2
Pregnancy test	X	X			X	X	X	X			See Section 8.2.5 and Section 10.2
Hepatitis serology, CD4 counts and viral load	X ^h	As clinically indicated									See Section 10.2 and Section 10.7
Hematology	X	X	X	X	X	X	X				See Section 10.2
Coagulation	X	As clinically indicated									See Section 10.2
Blood Chemistry	X	X	X	X	X	X	X				See Section 10.2

[figure not shown]
Evaluation ^a	Screening	Treatment Period ^b				End of Treatment	Observation Period ^c			Survival Phone Call Follow-up ^d	Notes	
		Cycle 1			Cycle 2 and beyond ^e	EOT Visit	Follow-Up	Follow-Up	Follow-Up	Phone Call FU		
							Visit 1	Visit 2	Visit 3+			

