 2. Participants who discontinue study treatment **with PD** will be followed for safety in the Follow-Up Visit 1 occurring 3 months \pm 7 days from last IMP administration, before moving to the Survival Phone Call Follow-Up Period.

Participants who move into the **Survival Phone Call Follow-Up Period** will be contacted by telephone every 3 months \pm 14 days to assess for survival status. Updated survival status may be requested by the Sponsor at any time during the study. Survival Phone Call Follow-up will continue until death, participant request to discontinue from follow-up, or cut-off date for the given cohort final analysis has been reached, or upon cancellation of Survival follow-up in the given cohort at the discretion of the Sponsor at any prior timepoint whichever occurs first.

The cohort cut-off for the primary ORR endpoint analysis for each individual cohort is estimated to be approximately 9 months from the date of the last participant first infusion. This would allow the possibility to observe the response of the last participant for 6 months, assuming there is a response at first treatment assessment.

After the cohort cut-off date for the primary ORR analysis, participants can continue to receive IMP, if clinical benefit is observed, until full permanent discontinuation criteria described in **Section 7** are met and will continue to undergo all assessments as per the study schedule of activities.

For each cohort, the cut-off date for the final analysis (ie, analysis of secondary objectives and update of primary objective) will be 18 months from the corresponding cohort LPI. After this cut-off date for the final analysis, the participants of the given cohort still receiving study treatment in that specific cohort will be followed up as the cohorts after early termination described in **Section 10.1.9**.

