8.3.5 Pregnancy

- Details of all pregnancies in female participants and female partners of male participants will be collected after the start of study intervention and until 120 days (for Cohort A, B1, B2, B3, C, and D1) or 60 days (for Cohort D2) following cessation of study treatment, or 30 days following cessation of study treatment if the participant initiates another anticancer therapy.
- If a pregnancy is reported, the Investigator will record pregnancy information on the appropriate form and submit it to the Sponsor within 24 hours of learning of the female participant or female partner of male participant (after obtaining the necessary signed informed consent from the female partner) pregnancy.
- Abnormal pregnancy outcomes (eg, spontaneous abortion, fetal death, stillbirth, congenital anomalies, ectopic pregnancy) are considered SAEs and will be reported as such.
- The participant/pregnant female partner will be followed to determine the outcome of the pregnancy. The Investigator will collect follow-up information on the participant/pregnant female partner and the neonate, and the information will be forwarded to the Sponsor.
- Any post-study pregnancy-related SAE considered reasonably related to the study intervention by the Investigator will be reported to the Sponsor as described in [Section 8.3.4](#). While the Investigator is not obligated to actively seek this information in former study participants/pregnant female partner, he or she may learn of an SAE through spontaneous reporting.
- Any female participant who becomes pregnant while participating in the study will discontinue study intervention.

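### Pregnancy tests are required about every 30 days to day 120 after the last dose (day 60 in Cohort D2), but the Schedule of Activities has no visit near day 60 or day 120 and marks a 6-month test that the text does not require

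*Protocol*

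**What the plan says.** **Text rule.** Protocol Section 8.2.5 states of women of childbearing potential that each "must have a negative urine pregnancy test result within 72 hours prior to first IMP administration of each cycle, at EOT and every 30" (counted in days, ±7). Testing ends at day 120 after the last dose, except in Cohort D2, where it ends at day 60. Appendix 2 (Section 10.2), note e, gives the same rule.

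**Table.** The master SoA (Section 1.3) has six marks in the pregnancy-test row: screening, Cycle 1 Day 1, Day 1 of later cycles, EOT, Follow-Up Visit 1 and Follow-Up Visit 2. The three post-treatment columns are timed as follows:
- EOT: "30 days (+/- 7 days) after last IMP or at initiation of further therapy"
- Follow-Up Visit 1: "3 months after last IMP admin ±7 days"
- Follow-Up Visit 2: 6 months after the last administration, ±7 days

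The substudy 01 (Cohort A) SoA has the same marks. In both tables the notes column of this row refers the reader to Sections 8.2.5 and 10.2.

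**Follow-up paths.** Under Section 4.1, participants who stop with PD attend Follow-Up Visit 1 "before moving to the Survival Phone Call Follow-Up Period", which consists of telephone contacts about survival.

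**Which source governs timing.** Section 8.2.4 points to the SoA for when and how often laboratory tests are done, and requires Appendix 2 tests to follow the SoA. Section 8 makes adherence to the SoA mandatory.

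**Pregnancy collection period.** Section 8.3.5 uses the same end dates: "Details of all pregnancies in female participants and female partners of male participants will be collected after the start of study intervention and until 120" (in days; 60 in Cohort D2). It shortens this to 30 days if the participant starts another anticancer therapy.

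**The concern.** The text and the table give different post-treatment test dates, and the protocol makes both binding. The 120-day (or 60-day) period is also the contraception period in inclusion criterion I 03 and the pregnancy collection period in Section 8.3.5. Pregnancy is an adverse event of special interest that must be reported to the sponsor immediately (Section 8.3.8).

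A site that books visits from the SoA has nothing prompting a test near day 60 or at the end of the 120-day period. A site that works from Section 8.2.5 does have that prompt. The two sites would collect different data on the same safety question. The first would accumulate deviations from Section 8.2.5 that come from the document and not from its conduct.

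**Working it through.** There is no sample size, power or error rate to reproduce. The check sets the windows required by the text against the SoA windows.

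**Inputs and assumptions**
- Text: every 30 (±7) days to day 120, or to day 60 in Cohort D2 (Section 8.2.5; Appendix 2 note e). The 30-day steps are counted from the last dose, with EOT as the day-30 test.
- SoA: EOT at 30 ±7 days, Follow-Up Visit 1 at 3 months ±7 days, Follow-Up Visit 2 at 6 months ±7 days (Section 1.3, master and substudy 01).
- 3 months is taken as 90 to 92 days and 6 months as 181 to 184 days.

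**Windows**
- Text: 30 ± 7 = days 23–37; 60 ± 7 = days 53–67; 90 ± 7 = days 83–97; 120 ± 7 = days 113–127.
- Follow-Up Visit 1: 90 − 7 = 83 to 92 + 7 = 99.
- Follow-Up Visit 2: 181 − 7 = 174 to 184 + 7 = 191.

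| Test due under the text | Text window | SoA visit with a pregnancy mark |
|---|---|---|
| Day 30 | 23–37 | EOT, days 23–37 |
| Day 60 (last one in Cohort D2) | 53–67 | none |
| Day 90 | 83–97 | Follow-Up Visit 1, days 83–99 |
| Day 120 | 113–127 | none |
| Not required | – | Follow-Up Visit 2, days 174–191 |

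**Results**
1. The SoA has a visit for 2 of the 4 required post-treatment tests. This holds with or without PD, because the next visit after 3 months is at 6 months.
2. The earliest 6-month test is 174 − 127 = 47 days after the last required window closes, so it cannot serve as the day-120 test.
3. With PD, Follow-Up Visit 1 is the last on-site visit. The last marked test then falls between 120 − 99 = 21 and 120 − 83 = 37 days before day 120, or about 3 to 5 weeks.
4. On the master SoA, Cohort D2 has a visit for 1 of its 2 required tests. The day-60 test, which closes its period, is the one without a visit.

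**Does another section settle it?** Inclusion criterion I 03 refers to Appendix 4 for testing during and after treatment, but Appendix 4 gives no test dates. Section 8.3.5 sets a collection period that ends at 30 days once another anticancer therapy starts; Section 8.2.5 has no matching exception. Neither section supplies the missing dates.

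**The case against.** The strongest reply is that the SoA row is not silent. Its notes column points to Sections 8.2.5 and 10.2, where the 30-day rule appears twice in the same terms. Other rows also rely on notes: urinalysis is marked at each cycle but limited by footnote to every 4 cycles, and Appendix 2 note a thins hematology and chemistry after Cycle 12. A careful site would follow the pointer and arrange a urine test.

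This stands in part. It shows that the tests are still required and that a site can find the rule. It does not close the gap. In the other rows the note reduces the number of marked visits, whereas here it would have to add dates that have no column. It also does not explain the 6-month mark.

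A reader might draw four stronger conclusions, which the documents do not support:
- **That the text and the table exclude each other.** They do not. A site can do the marked tests and add tests near days 60 and 120.
- **That pregnancies go undetected.** A continuing pregnancy begun before about day 60 would ordinarily show at the 3-month test. One begun by day 120 would ordinarily show at 6 months in participants who reach that visit. The main effect is delay. The exposed interval is from Follow-Up Visit 1 to day 120 in participants with PD, and even there Sections 8.3.5 and 8.3.8 require pregnancies to be reported however they are found. Where new anticancer therapy has started, the collection period in Section 8.3.5 has already ended at 30 days.
- **That the PD pathway causes the gap.** Days 60 and 120 lack a visit for everyone. PD only removes the later visit as well.
- **That Cohort D2 certainly has no closing visit.** Its substudy SoA is not shown and may differ from the master.

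**Conclusion.** The inconsistency is real and lies in the current text. For all participants, two of the four post-treatment pregnancy tests required by Section 8.2.5 and Appendix 2 note e have no visit in the master or substudy 01 SoA, and the 6-month mark corresponds to no required test. For participants with PD the last marked test is about 3 to 5 weeks before day 120. Because Section 8.2.4 binds the timing of these tests to the SoA, a site scheduling from the table may miss or delay them. That every such site would do so is not shown, since the row cross-refers to Section 8.2.5.

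The conclusion assumes that the 30-day steps run from the last dose and that months are calendar months. For Cohort D2 it rests on the master SoA alone. The point concerns safety scheduling in women of childbearing potential and changes no efficacy endpoint or analysis. It should be corrected, because the rule is a stated safety requirement and the correction is inexpensive.

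**What to change.** Reconcile four places: the pregnancy-test rows of the master and substudy SoAs, Section 8.2.5, Appendix 2 note e, and the collection period in Section 8.3.5. One set of post-treatment test dates should apply per cohort. Each date should have a place in the SoA, as a column or an explicit footnote, including for participants who move to telephone follow-up after PD.

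State whether the 30-day limit that Section 8.3.5 applies after new anticancer therapy also applies to testing. Correct the reference in inclusion criterion I 03, since Appendix 4 holds no test dates. Check the Cohort D2 SoA against the same list.

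Which schedule applies, and what becomes of the 6-month mark, is for the sponsor to decide. The cost is wording in the SoA and its cross-references. If the sponsor keeps the text rule, it adds no test beyond those the text already requires.

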8.3 ADVERSE EVENTS (AES), SERIOUS ADVERSE EVENTS (SAES) AND OTHER SAFETY REPORTING

The definitions of adverse events (AEs) and serious adverse events (SAEs) can be found in Appendix 3 ([Section 10.3](#)). The definition of AESI is provided in [Section 8.3.8](#).

AE will be reported by the participant (or, when appropriate, by a caregiver, surrogate, or the participant's legally authorized representative if allowed by local regulations).

The Investigator and any qualified designees are responsible for detecting, documenting, and recording events that meet the definition of an AE or SAE and remain responsible for following up AEs that are serious, considered related to the study intervention or study procedures, or that caused the participant to discontinue the study intervention (see [Section 7](#)).

The method of recording, evaluating, and assessing causality of AEs and SAEs and the procedures for completing and transmitting SAE reports are provided in Appendix 3 ([Section 10.3](#)).

8.3.1 Time period and frequency for collecting AE and SAE information

All AEs, including adverse events of new onset, as well as worsening of baseline signs and symptoms will be collected throughout study period, from the signing of the informed consent form (ICF) until **30 days** following cessation of study treatment.

All SAEs and AESIs will be collected throughout the study period, from the signing of the informed consent form (ICF) until **90 days** following last administration of study treatment.

All SAEs and AESI will be recorded and reported to the Sponsor or designee immediately and under no circumstance should this exceed 24 hours, as indicated in Appendix 3 ([Section 10.3](#)). The Investigator will submit any updated SAE data to the Sponsor within 24 hours of it being available.

Investigators are not obligated to actively seek information on AEs or SAEs after conclusion of the study participation. However, if the Investigator learns of any SAE, including a death, at any time after a participant has been discharged from the study, and he/she considers the event to be reasonably related to the study intervention or study participation, the Investigator must promptly notify the Sponsor.

8.3.2 Method of detecting AEs and SAEs

Care will be taken not to introduce bias when detecting AEs and/or SAEs. Open-ended and non-leading verbal questioning of the participant is the preferred method to inquire about AE occurrences.

